#### 10.4.2 Analysis of the Primary Endpoint

The pharmacokinetic parameters of Cmax, Ctrough, Tmax, AUC0-28days and AUC0- $\infty$  will be assessed from participants who submitted at least 75% valid pharmacokinetic blood samples. The data will be investigated using exploratory statistics. Means, medians, Standard

Deviations and Coefficients of Variation will be calculated for each administration and will be tabulated.

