### 3 OBJECTIVES AND PURPOSE

#### 3.1 PRIMARY OBJECTIVES

To determine the PK parameters of  $C_{max}$ ,  $T_{max}$  and AUC for the 1st and 6th dose of Vivitrol IM 380 mg, and  $C_{trough}$  for the 1st through 6th dose.  $C_{trough}$  is defined as the naltrexone level obtained 28 days after each dose. PK parameters will be collected over a treatment period of 196 days.

Primary outcomes used to determine these properties will be based on results from plasma concentration of NTX and 6 $\beta$ N as ascertained from blood samples taken at the following time points:

- Day 0 (predose, +1, 2, 4, 8, 12 & 24 hours), 1.5, 1.75, 2, 3, 5, 7, 10, 14, 17, 21, 24, 28,
- Day 56, 84, 112 days,
- Day 140 (predose +1, 2, 4, 8 & 12 hours), 141, 141.5, 141.75, 142, 143, 145, 147, 150, 154, 157, 161, 164, 168, 182, and 196 days

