### 4.2 STUDY ENDPOINTS

#### 4.2.1 *Primary Endpoint*

- The collection of at least 75% of the PK blood samples including respective day 28 blood collections for 1st and 6th injection phase.

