### 5.3 STRATEGIES FOR RECRUITMENT AND RETENTION

#### 5.3.1 *Target Sample Size*

Recruitment into the study will be solely offered to the 19 participants who have completed the previous study GM 0017. Up to 15 participants from GM 0017 will be targeted for recruitment to this study. We expect that 12 of the 15 participants will complete the study (80%), which is providing at least 75% valid PK blood samples including Day 28 and Day 168 Vivitrol trough levels.

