## 10 STATISTICAL CONSIDERATIONS

### 10.1 STATISTICAL AND ANALYTICAL PLANS

NTX (and 6 $\beta$ N) plasma concentration data will be explored by Non-Compartmental Analysis (NCA). Mean, median, standard deviation and coefficient of variation of parameters such as AUC0-28days, Ctrough, and Cmax will be reported for each day for which the parameter is available, which is the primary objective of this study. The Accumulation Ratio (AR) of these parameters comparing the sixth with the first administration will inform us if there is accumulation of NTX (and 6 $\beta$ N) and if this accumulation is substantial. This is a secondary objective of this study.

Comparison of the cumulative AUC0-28days, as well as overall Cmax and Ctrough during six consecutive Vivitrol administrations with previously determined 6-month data after OLANI (as determined in study GM0017) will inform us about bioequivalence of the two formulations. This is an exploratory objective of this study. Appropriate paired statistics will be used to compare the first with the sixth Vivitrol administration and to compare 6 months of Vivitrol with six months of OLANI.

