### 10.3 ANALYSIS DATASETS

The analysis will be performed based on Intention-to-Treat and Per-Protocol in all participants enrolled. Assessment of primary outcomes will be performed on participants who complete at least 75% of applicable time points.

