### 10.4 DESCRIPTION OF STATISTICAL METHODS

#### 10.4.1 General Approach

Pharmacokinetic parameters will be assessed from the NTX and 6 $\beta$ N plasma data using PK software (Phoenix Winnonlin, Princeton, NJ) and expressed and tabulated as a mean, median, standard deviation and co-efficient of variation for each administration of Vivitrol.

Participants who submitted at least 75% valid pharmacokinetic blood samples from all study arms shall be measured for pharmacokinetic parameters of Cmax, Ctrough, Tmax, AUC0-28days and AUC0- $\infty$ .

Accumulation of NTX and its metabolite is investigated using the Accumulation Ratio (AR) for AUC0-28days, AUC0- $\infty$ , Cmax and Ctrough. An accumulation ratio of 1 (e.g., AUC0-28days, 6th administration / AUC0-28days, 1st administration) indicates that there is no accumulation.

As an exploratory endpoint we will also compare the cumulative AUC0-28days during 6 consecutive administrations of Vivitrol with the AUC0-6months after OLANI, which was determined for each of these patients in study GM0017. In addition, Cmax and Ctrough will be compared for both formulations. Comparisons will be done using the ratio of the geometric mean of these parameters for each formulation.

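### Section 10 admits participants to dose-specific PK summaries by one participant-level 75% sample count, with its terms undefined and no minimum data per dose

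*Combined protocol and SAP*

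**What the plan says.** Section 3.1 sets the objective by dose: Cmax, Tmax and AUC for doses 1 and 6, and Ctrough for all six doses, where the trough "is defined as the naltrexone level obtained 28 days after each dose". Section 10.4.2 tabulates the results separately by administration.

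Entry to those tables is decided once per participant:

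- Section 10.3: "Assessment of primary outcomes will be performed on participants who complete at least 75% of applicable time points".
- Section 10.4.1: "Participants who submitted at least 75% valid pharmacokinetic blood samples from all study arms shall be measured for pharmacokinetic parameters", although the study has a single arm.
- Section 10.4.2: the parameters "will be assessed from participants who submitted at least 75% valid pharmacokinetic blood samples".

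The words 'applicable' and 'valid' are not defined. Other text bears on the rule without settling it:

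- Section 10.3 also states: "The analysis will be performed based on Intention-to-Treat and Per-Protocol in all participants enrolled".
- Section 10.1 says that summary statistics "will be reported for each day for which the parameter is available, which is the primary objective of this study", with no minimum data for a parameter to count as available.
- Section 4.2.1 gives the primary endpoint as "The collection of at least 75% of the PK blood samples including respective day 28 blood collections" for the first and sixth injection phases.
- Section 5.3.1 describes completing the study, "which is providing at least 75% valid PK blood samples including Day 28 and Day 168 Vivitrol trough levels". Section 10 does not repeat this trough condition.
- Section 10.5 sets a target of 12 participants reaching 75% of collection time points.
- Section 10.4.11 lists individual PK data in the report appendices.

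**The concern.** A dose-1 Cmax or a Day 28 trough depends only on samples taken around that dose. An overall sample count ties its use to attendance months later, and it lets good attendance elsewhere stand in for missing samples at the dose being summarised.

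Two things are at stake. First, usable dose-1 profiles and early troughs may be left out of the summaries, so that those summaries describe only people who stayed into the sixth dose. Second, sparse dose-6 profiles may enter dose-6 Cmax, Tmax and AUC0-28, and through them the accumulation ratios in sections 10.4.1 and 10.4.3. The study is meant to supply reference-product values for OLANI (section 4.1), so who contributes to each value should be fixed in advance.

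**Working it through.** **Inputs.** Sampling times: section 3.1. Total samples: section 7.2.3. Expected completion: 12 of 15 (section 5.3.1). The Protocol Summary and section 7.3.7 still show 6 and 4 participants; those figures are not used here.

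**Reproducing the plan's total.** Dose 1, Day 0 predose to Day 28: 19. Days 56, 84 and 112: 3. Dose 6, Day 140 predose to Day 168: 19. Days 182 and 196: 2. Sum: 19 + 3 + 19 + 2 = 43, and 43 × 9 mL = 387 mL, as section 7.2.3 states.

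**Threshold on the whole-study base.** 0.75 × 43 = 32.25, so 33 samples are needed and 10 may be missed.

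**Early leaver with no other missed sample.**

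- After Day 28: 19/43 = 44.2%.
- After Day 112: 22/43 = 51.2%.
- After the Day 140 predose sample: 19 + 3 + 1 = 23, and 23/43 = 53.5%. This person has all 19 dose-1 samples and the troughs at Days 28, 56, 84, 112 and 140.
- After Day 141: 29/43 = 67.4%.

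The schedule also has a naltrexone sample at screening (section 7.3.1) and PK blood at the early-termination visit (Table 7-1). If both count, with the screening sample added to the base, the Day 140 leaver has 25/44 = 56.8% and the Day 141 leaver 31/44 = 70.5%. Both still fail.

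Near Day 142 the answer depends on those two samples: 32/43 = 74.4% (fails) without them, 33/43 = 76.7% (passes) with early termination, 33/44 = 75.0% (passes) with screening.

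**Sparse dose-6 profile.** Nine post-dose inpatient samples are due at dose 6: 1, 2, 4, 8 and 12 hours, then Days 141, 141.5, 141.75 and 142. Missing only these leaves 43 − 9 = 34, and 34/43 = 79.1%, which passes. The Day 28 and Day 168 troughs are both present, so the condition in sections 4.2.1 and 5.3.1 is also met. The dose-6 profile then has 19 − 9 = 10 of 19 samples (52.6%), with nothing between predose and Day 143.

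**The two cases under each reading of the base.**

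| Base of the 75% | Leaves after Day 140 predose | No post-dose inpatient samples at dose 6 |
|---|---|---|
| All 43 scheduled | 23/43: excluded from everything | 34/43: admitted to everything |
| Samples due before leaving | 23/23: admitted | 34/43: admitted (all 43 were due) |
| Each dose's 19 samples | 19/19 at dose 1: admitted there | 10/19 at dose 6: excluded there |

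**Size.** Expected non-completers: 15 − 12 = 3. If all three leave between Day 28 and about Day 141 with usable dose-1 data, dose-1 n is 12. At the same SD, the standard error ratio is √(15/12) = 1.12. For an assumed range of 1 to 5 such leavers it runs from √(15/14) = 1.04 to √(15/10) = 1.22. The error in dose-6 AUC0-28 from a sparse profile cannot be sized from the documents.

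**The case against.** The strongest reply is that the worst reading need not be the intended one. 'Applicable' in section 10.3 could mean samples due before leaving, or samples for the parameter in question, and section 4.2.1 could be read as 75% within each injection phase. Section 10.5, which favours a whole-study base, is a completion target and not an analysis-set rule. This stands as far as it goes. But section 10 adopts none of these readings, and the table above shows that they admit different people. The due-before-leaving reading also does nothing about the sparse dose-6 profile.

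Four stronger conclusions might be inferred, and the documents do not support them:

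- *A one-sample cliff at Day 142/143.* It disappears if the screening or the early-termination sample counts, and the plan does not say whether they do.
- *Someone leaving at Day 143 enters the dose-6 summaries with a truncated profile.* The Day 168 condition in sections 4.2.1 and 5.3.1 would prevent this if it is applied.
- *Valid data are thrown away.* Section 10.4.11 keeps individual values in the listings. The loss is from the summaries only.
- *Dose-1 results will be biased.* That needs leaving to be related to tolerability or exposure, and nothing in the documents shows that it is.

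It is also fair to say that a participant admitted for intensive sampling is unlikely to give no post-dose blood. The case shows what the count permits; it is not a forecast. Section 10.2 states no hypotheses, so no error rate is affected.

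**Conclusion.** The point holds and should be fixed. Three sections gate dose-specific parameters by one participant-level count whose terms are undefined, and section 10 sets no minimum data for any dose. On a base of 43 samples, anyone leaving after Day 28 and before about Day 141 is left out of dose-1 and early-trough summaries to which they could contribute. The same count can admit a dose-6 profile with 10 of 19 samples.

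The illustrative cost is dose-1 n of 12 instead of 15 and a standard error about 12% larger. It rests on the whole-study base, on all three expected non-completers leaving in that window with usable dose-1 data, and on an unchanged SD. The study is descriptive, so the consequence is less precise and less clearly defined reference values, not a failed test. My confidence is moderate, because a per-phase intention would remove most of the problem once written down.

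**What to change.** In sections 10.3, 10.4.1 and 10.4.2, replace the single count with evaluability by dose and parameter, fixed before concentrations are seen:

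- **Ctrough:** everyone with that dose's 28-day sample.
- **AUC0-28:** participants with at least 75% of that dose's 19 samples (0.75 × 19 = 14.25, so 15), including its 28-day sample. This applies the plan's own percentage at dose level; the sponsor may justify another figure.
- **Cmax and Tmax:** participants meeting a sponsor-stated minimum of early-phase samples for that dose.
- **Accumulation ratio:** participants evaluable for that parameter at both doses compared.

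Keep 75% of scheduled study samples only as the completion measure (sections 5.3.1, 10.4.6 and 10.5). State its denominator, what makes a sample valid, and whether screening and early-termination samples count. Align section 4.2.1 and the intention-to-treat/per-protocol sentence in section 10.3 with these definitions, and report n for every parameter.

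The cost is protocol and SAP wording, with no added samples or visits. The drawback is that n will differ between tables and must be shown in each.

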#### ***10.4.3 Analysis of the Secondary Endpoint(s)***

We will calculate the Accumulation Ratio (AR) for  $AUC_{0-28days}$ ,  $C_{max}$  and  $C_{trough}$  by comparing the parameter after one administration with the same parameter after another, e.g.,  $AUC_{0-28days, 6th administration} / AUC_{0-28days, 1st administration}$ . An AR of 1 (or a value close to 1) indicates little to no accumulation.

This analysis will be accompanied by visual inspection of the plasma concentration time curves of NTX and its metabolite, which will be plotted graphically. The visual inspections and comparisons of the curves are exploratory endpoints of this study.

Visual inspection of the curves will also inform us if the plasma concentration time profile after the first administration is similar to that after the sixth administration of Vivitrol.

Visual inspection of the Vivitrol curves and comparison with the visual inspection of the OLANI (as determined in GM0017) curves in the same patients might also inform us if earlier identified rapid metabolizers of the OLANI formulation are also rapid metabolizers of the Vivitrol formulation.

Use of opioids, cocaine, marijuana, and alcohol for each day of the study will be determined based on results of urine toxicology and self-report. Proportion of days with substance use for each participant will be summarized.

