## V. PROTOCOL SUMMARY

Title:	A PHARMACOKINETIC STUDY OF VIVITROL IN HEALTHY PARTICIPANTS
Overview:	
This is a Phase I, single-center, single arm, open-label study, to establish the pharmacokinetic (PK) parameters of Vivitrol 380 mg IM injection (IP), a US Food and Drug Administration (FDA) approved medication. Participants will be healthy volunteers with no significant medical or mental health disorders, who have completed participation in clinical trial GM 0017 (i.e. have received the OLANI treatment and have subsequently provided two consecutive plasma levels of naltrexone (NTX) <0.1ng/mL).
 
This study will examine the PK profile of Vivitrol IM 380 mg over 6 doses for a treatment period of 196 days. Intense sampling will occur after the 1st and 6th dose of Vivitrol. Participants will be without a DSM 5 - Substance Related Disorders classification. Participants will be required to undergo a Naloxone Challenge Test (NCT) to confirm opiate naïvety before administration of the IP. No randomization will occur.
 
Note: In the future, an expansion of this protocol is planned in order to include additional participants that initially receive 2 doses of Vivitrol followed by the OLANI treatment (i.e. the ‘cross-over’ group). This expansion may occur under this same protocol ID or a new protocol ID.

Objectives:	
Primary:
 
 
To determine the PK parameters of <math>C_{max}</math>, <math>T_{max}</math>, <math>C_{trough}</math> (Day 28), and AUC for the 1st and 6th dose of Vivitrol IM 380mg.
 
 
Secondary:
 
 
To determine steady state characteristics and demonstrate no accumulation between repeat doses.
 
To establish the safety and tolerability of the NTX injection over 6 months.
 

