Endpoint:	
Primary:
 
 
PK parameters, including <math>C_{max}</math>, <math>C_{trough}</math> (Day 28), and AUC
 
 
Secondary:
 
 
To demonstrate no accumulation following repeat doses of Vivitrol IM 380 mg.
 
 
Safety endpoints will be captured through 6 months and will include the incidence of adverse events (AEs) including:
 
 
deaths
 
serious adverse events (SAEs)
 
AEs leading to discontinuation
 
common AEs
 

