#### 3.2 SECONDARY OBJECTIVES

- To confirm no accumulation between repeat doses
- To determine the safety and tolerability of Vivitrol over 196 days.

Safety endpoints will be captured throughout and will include the incidence of AEs including:

- deaths
- SAEs
- AEs leading to discontinuation
- common AEs
- AEs of special interest (injection site reactions and hepatic effects)
- laboratory abnormalities (absolute values and changes over time in laboratory parameters)
- the proportion of participants who discontinue treatment due to AEs)

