## 4 STUDY DESIGN AND ENDPOINTS

### 4.1 DESCRIPTION OF THE STUDY DESIGN

Participants who have completed the study end points of GM 0017 (i.e. two consecutive monthly plasma results <0.1 ng/mL for NTX) will be offered enrolment into the study.

Up to 15 participants will be recruited onto this arm with 12 expected to complete to full dosing and sampling schedule.

Participants will receive a 380 mg Vivitrol IM injection and blood samples will be taken according to the sampling schedule of Table 7-1. Subsequently, participants will be re-administered Vivitrol injections every 28 days for a total of 6 Vivitrol injections. Blood sampling will be performed as per Table 7-1. The administration of 6 repeated Vivitrol injections is to confirm the published findings that no accumulation of Vivitrol is evident after repeated injections and to allow a direct time frame comparison to future bioequivalence study with OLANI.

This PK information, including day 28 naltrexone trough level, is needed so that Vivitrol can be used as the reference product for previous and future studies of OLANI.

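### The stated aim is to demonstrate no accumulation, but the accumulation ratio is read as a point value near 1 and no interval is planned for it

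*Combined protocol and SAP*

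**What the plan says.** **The aim.** The Protocol Summary lists as a secondary objective "To determine steady state characteristics and demonstrate no accumulation between repeat doses" and as a secondary endpoint "To demonstrate no accumulation following repeat doses of Vivitrol IM 380 mg". Section 3.2 has "To confirm no accumulation between repeat doses". Section 4.1 gives this as one of two reasons for six injections: "The administration of 6 repeated Vivitrol injections is to confirm the published findings that no accumulation of Vivitrol is evident after repeated injections".

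**The reading rule.** Section 10.4.1 says that an AR of 1, for example dose 6 over dose 1 for AUC0-28days, "indicates that there is no accumulation". Section 10.4.3 widens this: "An AR of 1 (or a value close to 1) indicates little to no accumulation". The AR is accompanied by visual inspection of the concentration curves, which 10.4.3 classes as exploratory. Section 10.1 says that the AR will also show whether any accumulation is substantial, without a threshold.

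**Other statistics.** Section 10.1 adds: "Appropriate paired statistics will be used to compare the first with the sixth Vivitrol administration". No test, scale, level or interval follows. Section 10.2 gives the hypotheses as not applicable. The PK summaries named are mean, median, SD and CV. Confidence intervals appear only in 10.4.6 (completion of blood collection) and 10.4.7 (baseline characteristics).

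**The concern.** To demonstrate or confirm an absence, the analysis must show how large an effect the data rule out. A point ratio does not show that. Two studies can both observe an AR of 1.00 while one excludes a 20% increase and the other does not; only the interval separates them.

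As written, the report could state that no accumulation was demonstrated without saying what increase remains compatible with the data. The Vivitrol PK results are meant to serve as the reference for OLANI studies and an application (Sections 2.1.4, 2.2 and 4.1), so the statement is likely to be carried forward without its uncertainty.

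**Working it through.** **1. The plan's own figure.** Section 5.3.1 expects 12 of 15 participants to complete (80%): 15 × 0.80 = 12, which reproduces and agrees with Sections 4.1 and 10.5. The plan has no power, margin or precision figure for the AR to reproduce.

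**2. Inputs for the illustration.**
- n = 12 completers (Sections 4.1, 5.3.1, 10.5).
- Within-participant CV: not in the documents. 20%, 30% and 40% are assumed.
- Log-normal parameters, with independent within-participant errors of equal variance at doses 1 and 6.
- Observed AR = 1.00, the value that the plan reads as no accumulation.

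**3. Formulas.** Log-scale within-participant SD: s = √ln(1 + CV²). Standard error of the mean log ratio: SE = s × √(2/n). 90% CI: AR × exp(± t × SE), with t the 95th percentile on n − 1 degrees of freedom. For n = 12, t = 1.7959.

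| Assumed CV | s | SE (n = 12) | 90% CI around AR = 1.00 |
|---|---|---|---|
| 20% | 0.1980 | 0.0809 | 0.865–1.156 |
| 30% | 0.2936 | 0.1198 | 0.806–1.240 |
| 40% | 0.3853 | 0.1573 | 0.754–1.326 |

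For example, at 30%: 1.7959 × 0.1198 = 0.215, and exp(0.215) = 1.24.

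**4. Sensitivity to n.** If all 15 complete (t = 1.7613), the intervals are 0.880–1.136, 0.828–1.208 and 0.781–1.281. The Population entry of the Protocol Summary and Section 7.3.7 still speak of 4 completers. At n = 4 the interval would be 0.72–1.39 at CV 20% and 0.61–1.63 at CV 30%. The illustration uses 12, the figure in the design and sample size sections.

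**5. Could the paired statistics of 10.1 close the gap?** Not if they turn out to be a test of difference. Suppose the true AR were 1.25 (an illustrative value). The noncentrality is ln(1.25)/SE = 0.2231/SE, or 2.76, 1.86 and 1.42 at CV 20%, 30% and 40%. On 11 degrees of freedom, a two-sided 5% paired t-test then has power of about 71%, 40% and 25%. So about 29%, 60% or 75% of such studies would report no significant difference despite a 25% increase. A non-significant test would not demonstrate absence.

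**6. What else bears on accumulation.** Section 3.1 defines Ctrough for each of doses 1 to 6, sampled on Days 28, 56, 84, 112, 140 and 168. Section 10.4.3 defines the AR as one administration against another, with dose 6 over dose 1 as an example. A dose 6 to dose 1 contrast alone would leave four of the six troughs (doses 2 to 5) unused. The plan gives no interval for ratios from this series either.

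**The case against.** The strongest reply is that this is a descriptive, single-arm Phase I study of an approved product, with hypotheses declared not applicable. The analysis text is more cautious than the objectives: 10.1 says the AR will inform on accumulation, 10.4.1 says accumulation is investigated, and 10.4.3 speaks of little to no accumulation. On that view the mismatch lies mainly in the verbs of the Protocol Summary and Sections 3.2 and 4.1. This largely stands. It shows that rewording is the natural remedy, but it does not remove the need for an interval.

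A reader might infer that the plan relies on a point ratio and visual inspection alone. The documents do not support that: 10.1 promises a paired comparison of the first and sixth administrations, and six serial troughs will be reported. What is missing is the method and the interval.

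A reader might also infer that an increase of about a third would be missed. That rests on the highest CV assumed here; at 20% the upper limit is about 1.16. The documents give no CV, so the whole range carries equal weight.

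Nor do the documents require a fixed no-accumulation bound. In a study without hypotheses, a bound is the sponsor's choice.

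Finally, SD and CV are planned for each administration, and 10.4.11 puts individual PK data in the appendices. The SD and CV describe spread between participants at one dose, not the precision of a within-participant ratio. The individual data would let a reader rebuild an interval. That limits the harm, but it does not put the interval beside the claim.

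**Conclusion.** The point holds as a mismatch between the verb and the analysis. The protocol aims to demonstrate or confirm no accumulation, reads a point AR at or near 1 as showing it, leaves the paired method unnamed, and plans no interval for the AR. That finding depends on no assumption.

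Its size does depend on assumptions. With 12 completers, log-normal data, equal and independent within-participant errors, and an assumed CV of 20% to 40%, an observed AR of 1.00 leaves upper 90% limits of about 1.16 to 1.33. Whether such an increase is material is for the sponsor to judge.

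The severity is minor: no dosing or study decision in the protocol depends on this secondary objective, and a better analysis of the same data is available cheaply.

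**What to change.** In Section 10.4.3, for both NTX and 6β-naltrexol:

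- Analyse within-participant dose 6 minus dose 1 differences in log AUC0-28days, log Cmax and log Ctrough. Report the geometric mean AR with a 90% CI, and name this as the paired statistics of Section 10.1. Section 10.4.1 already uses a ratio of geometric means for the OLANI comparison, so the scale is consistent.
- Summarise Ctrough for doses 1 to 6, with ratios to the dose 1 trough and their intervals.
- Keep visual inspection as supportive.

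In the Protocol Summary and Sections 3.2 and 4.1, replace demonstrate and confirm with estimate, and base any statement about accumulation on the interval. If the sponsor prefers to keep the stronger verb, it should fix its own bound in advance and name the parameters to which it applies. With two analytes and three parameters there are six ARs, and 10.4.10 plans no multiplicity adjustment, so it should also say whether all the named ones must meet the bound.

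The cost is a protocol amendment, since Section 14.3 requires sponsor agreement and IRB approval for changes. No new samples, visits or participants are needed. The downside is that the no-accumulation claim may become an estimate with an interval.

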#### 2.1.1 *Metabolism of Naltrexone*

NTX is well absorbed orally (96%), but it undergoes a significant first pass metabolism resulting in only 5 to 40% oral bioavailability. NTX is extensively metabolized in humans. Production of the primary metabolite, 6 $\beta$ -naltrexol (6 $\beta$ N), is mediated by dihydrodiol dehydrogenase, a cytosolic family of enzymes. Two other minor metabolites are 2-hydroxy-3-methoxy-6 $\beta$ -naltrexol and 2-hydroxy-3-methoxy-naltrexone. NTX and 6-BN terminal half-life values have been reported as ranging from 2 to 10 hours for NTX and 7.5 to 13 hours for 6-BN. Both NTX and 6-BN are excreted primarily by the kidneys. There is a large amount of variation in the metabolism and PK of NTX. In one study, the enzyme kinetics of the formation of 6-BN from NTX using human liver cytosol preparation showed a 2.9 fold variability in Vmax, a 3.2 fold variability in Km and a 7.7 fold variability in intrinsic clearance. The systemic clearance of NTX supersedes the hepatic blood flow, suggesting the NTX is highly extracted and extra hepatic sites of drug metabolism exist.

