### ***7.2.2 Other Assays or Procedures***

#### **7.2.2.1 Naltrexone Blood Assay**

1 x 10 mL of whole blood in Na Heparin tubes (9 mL). Samples will be centrifuged for 15 min at 2,000 rpm. Plasma will then be extract and stored in suitable containers (1.5 mL Eppendorf's) for storage at -80°C for transport to WuXi laboratories under dry ice in batches for free (unconjugated) NTX and free (unconjugated) 6βN analysis.

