#### ***10.4.12 Exploratory Analyses***

No exploratory analysis will be conducted.

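### Section 10.4.3 judges only by eye whether OLANI rapid metabolizers are also rapid on Vivitrol, from depot curves that mix release with disposition and without a per-person measure

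*Combined protocol and SAP*

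**What the plan says.** Section 10.4.3 asks a question about individuals. The method is "Visual inspection of the Vivitrol curves and comparison with the visual inspection of the OLANI (as determined in GM0017) curves in the same patients", which "might also inform us if earlier identified rapid metabolizers of the OLANI formulation are also rapid metabolizers of the Vivitrol formulation". The section plots curves for NTX and its metabolite, but the OLANI sentence does not name the analytes. It adds that "The visual inspections and comparisons of the curves are exploratory endpoints of this study", whereas Section 10.4.12 states that "No exploratory analysis will be conducted".

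The document gives no definition, cut-off or metric for a rapid metabolizer; such people are taken as already known from GM 0017. The only numerical OLANI–Vivitrol comparison (Section 10.4.1) is a ratio of geometric means, a group result that cannot classify anyone.

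Both NTX and 6βN are assayed (Sections 3.1 and 7.2.2.1), non-compartmental analysis covers both (Sections 10.1 and 10.4.1), and individual PK data will be listed (Section 10.4.11). No metabolite-to-parent ratio is planned. On why metabolism matters, Section 2.1.1 says: "There is a large amount of variation in the metabolism and PK of NTX".

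**The concern.** A rapid metabolizer is someone with high clearance. With a slow-release product, a low or early-falling NTX curve can arise from high clearance, from slow or incomplete release, or from fast release that is exhausted early. Two products with different release mechanisms and different doses (OLANI 3.6 g in Section 5.1, Vivitrol 380 mg per injection) add to the difficulty.

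Judging the curves by eye gives no value for each person and no statement of how well the two products agree. The reading can therefore credit to metabolism what belongs to release, or the reverse, and nothing in the output would show it. What is at stake is the interpretation of one exploratory comparison. The primary PK objective and the sample size are untouched.

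**Working it through.** The plan states no figure on this point, so there is none to reproduce.

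**Inputs from the documents.** Terminal half-life 2 to 10 h for NTX and 7.5 to 13 h for 6βN; mainly renal excretion of both; 7.7-fold in-vitro variability in intrinsic clearance to 6βN (all Section 2.1.1). Dosing interval 28 days (Section 4.1). Expected completers 12 of 15 (Section 5.3.1).

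**Assumptions, since the documents give no values.** Linear kinetics; first-order release with half-life h = 7 days (varied from 3.5 to 60); the full dose reaching the circulation (varied to 60%); 70% of NTX clearance through 6βN. The model was run at both ends of the half-life ranges (2/7.5 h and 10/13 h).

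**Step 1: what curve height measures.** 28 days is 672 h, at least 672/10 ≈ 67 NTX half-lives. The level therefore follows release: C(t) ≈ R(t)/CL.

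**Step 2: release alone moves the NTX curve.** AUC over 0–28 days is about proportional to 1 − 2^(−28/h): 0.9375 at h = 7, 0.9961 at 3.5, 0.75 at 14 and 0.2764 at 60. Relative to 7 days that is 1.06, 0.80 and 0.29. The day-28 level is about proportional to (1/h)·2^(−28/h): relative to 7 days, 0.125, 2.0 and 1.35. The full model agrees closely.

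| Single change from base | NTX AUC 0–28 d | NTX day 28 | 6βN:NTX AUC ratio |
|---|---|---|---|
| Release half-life 3.5 d | 1.06–1.07 | 0.13 | 1.003–1.005 |
| Release half-life 14 d | 0.80 | 1.94–1.99 | 0.992–0.995 |
| Release half-life 60 d | 0.29 | 1.28–1.34 | 0.981–0.989 |
| Input reduced to 60% | 0.60 | 0.60 | 1.00 |
| 6βN formation clearance ×2 | 0.59 | 0.57–0.59 | 2.00 |
| Other NTX clearance routes ×2 | 0.77 | 0.76–0.77 | 1.00 |
| 6βN clearance ×0.5 | 1.00 | 1.00 | 1.99 |
| 6βN clearance ×2 | 1.00 | 1.00 | 0.50 |

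A 40% shortfall in input and a doubling of 6βN formation give almost the same NTX AUC (0.60 and 0.59). The NTX curve hardly distinguishes them; the ratio does (1.00 and 2.00).

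**Step 3: why the ratio behaves this way.** Over full exposure, with input F × Dose:
- AUC(NTX) = F·Dose/(CLf + CLother). Doubling formation gives 1/(1.4 + 0.3) = 0.59; doubling the other routes gives 1/(0.7 + 0.6) = 0.77.
- AUC(6βN) = AUC(NTX)·CLf/CLm.
- Ratio = CLf/CLm, where CLf is 6βN formation clearance and CLm is 6βN elimination clearance. F and Dose cancel. CLm does not, and CLother is absent.

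**Step 4: a further limit.** If hepatic formation is flow-limited, CL = Q·CLint/(Q + CLint). For a 7.7-fold range in CLint, a lowest CLint/Q of 0.5 gives CL/Q from 0.333 to 0.794 (2.4-fold). A lowest value of 10 gives 0.909 to 0.987 (1.1-fold). The ratio may then discriminate weakly. This bears on the hepatic part only, since Section 2.1.1 infers metabolism elsewhere too.

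**Step 5: attenuation in curve height (illustrative).** On the log scale, with release independent of clearance, independent between products and equally variable in each, the between-product correlation is var(CL)/[var(CL) + var(R)]. Equal variances give 0.5. Release four times as variable gives 1/(1 + 4) = 0.2, and a quarter as variable gives 1/(1 + 0.25) = 0.8. These hold even if clearance is perfectly reproducible. The variance ratios are assumed.

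**Step 6: precision at 12 completers.** Fisher z for r = 0.7: atanh(0.7) = 0.867, SE = 1/√(12 − 3) = 0.333, limits 0.867 ± 0.653, back-transformed to 0.21 and 0.91. This is the Pearson form and only approximates a Spearman interval.

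**The case against.** The strongest reply has four parts.

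- **Metabolite curves are plotted.** Poor release lowers both analytes, while faster 6βN formation lowers parent relative to metabolite, so a careful eye is not blind to the difference. This stands, at least for Vivitrol. It does not supply a per-person value or a measure of agreement, and the analytes shown for OLANI are not stated.
- **The text is hedged and exploratory.** It sets no rule and no decision follows from it. This stands and fixes the priority as low.
- **The answer leans on GM 0017.** How rapid metabolizers were identified is not visible here and might already use metabolite data. Whether per-participant 6βN exposure exists for OLANI is not shown either: Section 10.4.1 refers to each person's 6-month AUC without naming the analyte. This stands, so the OLANI half of the remedy must be conditional.
- **The gain is small.** The interval at 12 completers is wide, and the Vivitrol ratio could be computed later from the listings. Both are true. But an interval shows the uncertainty that inspection by eye leaves unstated, and a measure chosen in advance cannot be fitted to what the curves seem to show.

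A reader might also infer that the ratio cleanly separates release from metabolism. It does not. It removes release and dose but reflects 6βN formation relative to 6βN elimination. Section 2.1.1 describes 6βN as mainly renally excreted, so slow renal clearance would raise the ratio on both products and could look like a reproducible metabolic trait. Clearance by other routes is missed altogether.

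**Conclusion.** The concern holds as a low-priority improvement to an exploratory analysis. The only stated method is inspection of curves in which release and disposition are mixed. Under the assumptions above, release alone can change NTX AUC over 28 days from 1.07 down to 0.29 of its base value, and the day-28 level from 0.13 to about 2 times, with metabolism unchanged. The 6βN:NTX AUC ratio stays within 2%. These sizes rest on assumed release half-lives and linear kinetics, not on trial data.

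Two stronger readings are not supported. One is that this inspection decides whether low OLANI levels are a formulation problem: no section reports low OLANI levels or ties such a decision to the curves. The other is that correlations of 0.2, 0.5 or 0.8 are to be expected in this trial: they only illustrate the algebra.

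**What to change.** In Section 10.4.3, keep the curves as illustration and add, labelled exploratory:

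1. State how GM 0017 identified rapid metabolizers.
2. For each participant, report the molar 6βN:NTX AUC ratio on Vivitrol (doses 1 and 6, 0–28 days) beside NTX AUC. If GM 0017 holds per-participant 6βN data, report both for OLANI over a stated matched window.
3. Show a paired plot of the two products and a Spearman correlation with 95% CI.
4. State that the ratio removes release and dose, reflects 6βN formation relative to 6βN elimination, and misses non-6βN routes. Read it beside renal function; creatinine is already collected (Section 7.2.1).
5. If GM 0017 has no 6βN data, compare dose-normalised NTX AUC and say that release and metabolism are not separated.
6. Reconcile Section 10.4.12 with Section 10.4.3 and with the exploratory OLANI comparison in Sections 10.1 and 10.4.1.

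The cost is SAP wording and a few lines of analysis. On the Vivitrol side no extra blood or visits are needed. The drawback is a wide interval at about 12 completers, which should be reported as such.
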